**Control:** Usual care using balanced crystalloids (Iso-Lyte or Plasma-Lyte) only will follow Surviving Sepsis Campaign guidelines. Controls will receive 30 mL/kg (2100 mL in a typical 70 kg adult) of crystalloids within the first 3 hours. Crystalloid administration may be terminated before the entire dose has been administered if patients show clinical improvement, or if the treating clinician has concerns about circulatory overload. After the initial dose of crystalloids has been given, subsequent fluid resuscitation (crystalloid or colloid) will be given at the discretion of the treating clinician.

**Observational Arm:** Patients with suspected sepsis who do not meet the criteria for randomization or unable to obtain informed consent in a timely fashion (within 3 hours of research team being notified) will be enrolled in a prospective observational arm of the study. Baseline demographic and hospitalization data including the fluid therapy per the attending physician's discretion will be collected. Blood samples will also be collected at 0, 2, 3, 6, 12, and 24 hours upon determination of patients' eligibility for the observational study arm. A waiver of informed consent will be requested given that no intervention will be performed on the patient and that the study will be at minimal risk to the patient. The research team will attempt to obtain written informed consent from the patient or his/her legal authorized representative for 24 hours after patient enrollment into the observational study arm. If informed consent is denied by the patient or his/her legal authorized representative, no further data or blood samples will be collected and any data or blood samples collected prior to decline of participation will not be used in this study.

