**Endpoints of Resuscitation:** Fluid resuscitation in both the intervention and the control arms will be titrated to serial reassessments of the patient's volume status via blood pressure monitoring (MAP > 65 mmHg), urine output measurements (goal of  $\geq 0.5$  cc/kg/hr), CVP measurements (>8 mmHg), stroke-volume variation on hemodynamic monitors (such as the Vigileo), inferior vena cava (IVC) collapsibility index via bedside ultrasound, and lactate clearance (goal of  $\geq 50\%$  clearance after 6 hours of resuscitation). Serial laboratory examinations including lactate levels will be performed per standard of care in the ICU, until the lactate has normalized. Additional fluid support after the initial plasma or crystalloid bolus will be given at the discretion of the treating clinician, keeping in mind that septic shock patients in several randomized trials required 6-8L crystalloid per day.

**Co-interventions:** Both groups will receive standard care following Surviving Sepsis Guidelines, including procurement of blood cultures, administration of broad-spectrum antibiotics, transfusion of packed red blood cells for hemoglobin < 7 mg/dL, and use of vasopressors to maintain MAP > 65 mmHg.

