	T = 0	T = 2	T = EoR	T = 6	T = 12	T = 24
Serum Biomarkers	✓	✓	✓	✓	✓	✓

Serum biomarkers = syndecan-1, sTM, sFLT-1, VEGF, sRAGE, HMGB-1, IL-6, 8, 10, 1 $\alpha$ , 1 $\beta$ , vWF, tPA, NE, and epinephrine;  
EoR = End of Resuscitation (variable, depending on patient response to fluids)

resuscitation, time on vasopressors, time until lactate normalization, ventilator days, ICU-free days, and hospital length of stay. Organ dysfunction will be measured including acute lung injury and acute renal failure. Standardized definitions will be used as outlined in the method of operation used in previously conducted trials by our group. Potential harms of plasma administration will be assessed including symptomatic and asymptomatic venous thromboembolisms, transfusion-related allergic reactions, febrile non-hemolytic transfusion reaction, delayed-serological transfusion reactions, and transfusion-associated circulatory overload. Risk/safety evaluation will be performed at half recruitment (13 randomized patients).

**Blinding:** The healthcare provider will not be able to be blinded to the study intervention. The outcome assessors will be blinded when feasible, and the laboratory technicians and statisticians will be blinded.

**Sample Size:** We propose to enroll 26 patients (13 in each treatment arm) for the pilot randomized study to obtain unbiased estimates of treatment effect. We propose to enroll up to 100 patients to the observational study arm. Because this is a feasibility pilot study, we do not provide a power analysis for any outcomes since no formal hypothesis testing will be conducted. Instead, we will calculate estimates of treatment effect and 95% confidence intervals for all measures. We will also calculate probabilities of treatment benefit/harm using Bayesian analyses and conservative neutral priors. These estimates will inform the design of a future larger trial.

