**Statistical Analysis:** Because this is a pilot, efficacy trial, we will perform both a per-protocol and an intention-to-treat analysis. Both frequentist and Bayesian analysis will be performed. For the primary outcome and all continuous outcomes (using variable transformations if needed), we will use mixed models that include group and time period as covariates with a random subject effect. We will report group differences and 95% CIs from these models. For binary outcomes, a log binomial (or Poisson in case of non-convergence) will be used to estimate relative risks and 95% CIs. Hazard ratios and 95% CIs will be reported for time-to-event comparisons. For the Bayesian analysis, neutral conservative priors (that exclude large treatment effects almost never seen with medical interventions) will be used to estimate the probability of both benefits and harms, as defined by our primary and secondary outcomes.

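### The relative-risk rule for binary outcomes gives no usable estimate or 95% CI when an arm has no events, which is likely for the rare transfusion harms at 13 per arm (minor)

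*Combined protocol and SAP*

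**What the plan says.** All references are to the combined protocol and SAP.

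- **Statistical Analysis.** One frequentist rule covers all binary outcomes: "a log binomial (or Poisson in case of non-convergence) will be used to estimate relative risks and 95% CIs". Neither the interval method nor the variance estimator is named. Bayesian probabilities of benefit and harm under neutral priors are planned alongside.
- **Sample Size.** With 26 patients, 13 per arm, the plan gives no power calculation because it intends no formal tests. In their place it promises that "we will calculate estimates of treatment effect and 95% confidence intervals for all measures", and these are meant to inform a larger trial.
- **Outcomes text after Table 2.** The harms to be assessed are "symptomatic and asymptomatic venous thromboembolisms" and four transfusion-specific ones: "transfusion-related allergic reactions, febrile non-hemolytic transfusion reaction, delayed-serological transfusion reactions, and transfusion-associated circulatory overload".
- **Control.** "Usual care using balanced crystalloids (Iso-Lyte or Plasma-Lyte) only will follow Surviving Sepsis Campaign guidelines". After the first dose, "subsequent fluid resuscitation (crystalloid or colloid) will be given at the discretion of the treating clinician". Under Co-interventions, red cells may be given in both arms.

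No section says what is reported when an arm has no events. There is no exact method, correction, risk difference or counts-only rule.

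**The concern.** A relative risk needs events in both arms. The listed harms include reactions that normally require exposure to a blood product, and control patients start on crystalloid alone. With 13 patients per arm, an empty arm is then an ordinary result. The only fallback in the plan is triggered by non-convergence. That is a numerical condition, whereas the difficulty lies in the data.

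Because estimates and intervals take the place of tests in this pilot, the interval is the main frequentist statement about each harm. If the rule returns nothing usable, the analyst has to choose a method after seeing the counts.

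**Working it through.** **Inputs.** The 13 per arm is from Sample Size, and the block sizes under Randomization agree with it (5 × 4 + 6 = 26, or 13 each). The plan has no power, precision or harm-rate figure to reproduce. All event rates below are assumptions.

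**1. One arm empty.** Take 2/13 on plasma and 0/13 on control as an example.
- The maximum-likelihood relative risk is (2/13)/(0/13), which is infinite under either model.
- With a and b events in the two arms, the Wald variance of the log relative risk is 1/a − 1/13 + 1/b − 1/13 (log-binomial) or 1/a + 1/b (Poisson). Both are infinite at b = 0.
- In statsmodels, log-binomial gave a log relative risk of 20.5 (SE 12,220) and Poisson gave 20.4 (SE 11,460). Both 95% CIs were 0 to infinity. Both fits were flagged as converged, so the Poisson fallback would not be triggered, and it would not help.

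**2. Profile likelihood, same data (log-binomial).**
- Unconstrained log-likelihood: 2 ln(2/13) + 11 ln(11/13) = −5.581.
- At a relative risk of 0.683, the best-fitting risks are 0.0613 (plasma) and 0.0897 (control). The log-likelihood is 2 ln(0.0613) + 11 ln(0.9387) + 13 ln(0.9103) = −7.502.
- Deviance: 2 × (7.502 − 5.581) = 3.84, the 95% cut-off.
- The interval is therefore 0.68 to infinity: one informative limit only.

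**3. Both arms empty.** The relative risk is 0/0. The log-binomial fit printed 0 to infinity and the Poisson fit failed.

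**4. How often, equal assumed rates.** Let q = (1 − p)^13 be the chance that one arm is empty.

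| Assumed rate p | q | Exactly one empty, 2q(1 − q) | Both empty, q² | At least one, 1 − (1 − q)² |
|---|---|---|---|---|
| 2% | 0.769 | 36% | 59% | 95% |
| 5% | 0.513 | 50% | 26% | 76% |
| 10% | 0.254 | 38% | 6% | 44% |

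**5. How often, controls at an assumed 1%.** The chance of an empty control arm is 0.99^13 = 0.878.
- Plasma at 5%: exactly one arm empty 49%, both empty 45%.
- Plasma at 10%: exactly one arm empty 69%, both empty 22%.

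**6. What a risk difference gives (Miettinen-Nurminen).** The limits are the values d at which (observed difference − d)² / {[p₁(1 − p₁)/13 + p₂(1 − p₂)/13] × 26/25} = 3.841, with p₁ and p₂ fitted under p₁ − p₂ = d.
- 2/13 v 0/13: +15.4 points, 95% CI −10.0 to +42.8.
- 0/13 v 0/13: at the upper limit p₂ = 0 and p₁ = d, so 12.5d/(1 − d) = 3.841 and d = 3.841/16.341 = 0.235. The CI is −23.5 to +23.5 points.
- Exact 95% CI for one arm at 0/13: upper limit 1 − 0.025^(1/13) = 0.247, so 0 to 24.7%.

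**7. Coverage of that score interval (exact enumeration of all tables).**
- Used on every table: 99.7% (5% v 5%), 98.2% (10% v 10%), 99.96% (5% v 1%), 99.4% (10% v 1%).
- Used only when an arm is empty, and conditional on that: 96.1% at 10% v 10% and 93.3% at 12% v 12%.

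**The case against.** The strongest case against is that little is lost. The Bayesian analysis, with proper priors that rule out very large effects, gives a finite result with an empty arm. The primary outcome is a set of biomarkers analysed by mixed models. No stated decision uses a harm relative risk. In a table of 2/13 against 0/13 the counts carry most of the information, and the replacement interval is itself wide. The plan also never says Wald, so a profile-likelihood interval would be within its wording.

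Most of this stands, and it is why the point is minor. It does not remove the gap. The Bayesian result is not named as the zero-event fallback, its priors have no numbers, and frequentist intervals are promised separately for all measures. Profile likelihood would give one limit when one arm is empty and nothing when both are.

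A reader might also infer more than the documents support:
- **That mortality is affected.** The plan also provides hazard ratios for time-to-event comparisons, and no available text assigns mortality to the binary model. No figure for mortality is claimed here.
- **That controls cannot have transfusion reactions.** Later colloid and red cells are allowed, so a low control rate is plausible but zero is not guaranteed.
- **That venous thromboembolism is affected for the same reason.** It does not depend on transfusion. It is exposed only if it happens to be rare.
- **That a score interval used only for empty arms is safely conservative.** Step 7 shows that its conditional coverage can fall below 95%.

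**Conclusion.** The concern holds, and it is minor. The stated rule cannot give a usable relative risk and 95% CI when an arm has no events, and the Poisson fallback does not change that. At 13 per arm this is likely for rare harms: at least one arm is empty in 95%, 76% or 44% of trials at equal rates of 2%, 5% or 10%.

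The failure with an empty arm is a mathematical fact and rests on no assumption about rates. How often it happens rests wholly on assumed rates, because the documents give none. The loss is confined to the frequentist estimate and interval for sparse safety and other secondary binary outcomes. The biomarker primary outcome, binary outcomes with events in both arms, and the Bayesian probabilities of harm are not affected.

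**What to change.** Add to the Statistical Analysis section:

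1. For every listed harm, whatever the counts, report events and patients per arm and the risk difference with a score-type 95% CI (for example Miettinen-Nurminen).
2. When both arms have no events, add the exact 95% CI for each arm's risk (0 to 24.7% at 0/13).
3. Report a model-based relative risk for a harm in addition, and only when both arms have events.
4. For any other binary outcome with an empty arm, report the same quantities in place of the relative risk.

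Fixing the scale for harms in advance avoids a switch that depends on the data. It also keeps the score interval's overall coverage, which is about 98% or more at the assumed harm rates. Item 4 still depends on the counts, so there the conditional coverage can fall somewhat below 95% (93.3% at 12% v 12%).

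The cost is a few sentences. Harms will be on a different scale from other binary outcomes, and the intervals will be wide, as they must be with 13 per arm.

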#### **Informed Consent:**

Exception from Informed Consent will not be used in this trial. Written informed consent will be obtained from potential subjects or a legally authorized representative prior to randomization.

**Randomization:** Randomization will occur once the informed consent has been obtained. A 1:1 allocation will be used for the randomization. Subjects will be randomized to either the intervention arm (use of plasma) or the control arm (standard of care). Randomization will be performed using a computer-generated random sequence placed in opaque, consecutively-numbered, sealed envelopes kept in the locked Center for Translational Injury Research (CeTIR) office. A CeTIR research coordinator is available 24 hours a day, 7 days a week. Allocation will be 1:1. Patients will be stratified by enrollment location (STICU, ED, and Medical) in 5 blocks of 4 and 1 block of 6 for a total of 26 patients. **[Figure 4].**

**Figure 4** – Flow diagram depicting patient screening, enrollment, and randomization.

**Intervention:** Initial resuscitation with plasma will be 10 mL/kg (700 mL in a typical 70 kg adult). Traditional doses of plasma, when used to correct coagulopathy range from 10-15 mL/kg. The plasma will be administered at a rate of 2-3 mL/kg/hr (140-210 mL/hr in a typical 70 kg adult). A research physician will be at bedside to follow patient resuscitation. Plasma administration may be terminated before the entire dose is administered if patients show clinical improvement, or if the treating clinician has concerns about circulatory overload. After the initial dose of plasma has

been given, subsequent fluid resuscitation (crystalloid or colloid) will be given at the discretion of the treating clinician.

The blood bank will have thawed plasma available on call as soon as an eligible patient has been identified. Type and screen will be performed concurrently to provide donor-matched plasma for subjects randomized to intervention group. For patients who proceed to the operating room during fluid resuscitation, the anesthesiology team will continue fluid administration per study protocol.

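### A neutral prior that excludes large effects is ill suited to transfusion-specific harms: it understates the probability and size of harm when events are few, and its width is not stated.

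*Combined protocol and SAP*

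**What the plan says.** Two places set the Bayesian rule. Sample Size states: "We will also calculate probabilities of treatment benefit/harm using Bayesian analyses and conservative neutral priors". Statistical Analysis repeats it with a description of the priors: "priors (that exclude large treatment effects almost never seen with medical interventions) will be used to estimate the probability of both benefits and harms", with benefit and harm "as defined by our primary and secondary outcomes". Neither place gives a distribution, a scale, a prior for the control risk or a sensitivity prior, and neither separates harms from efficacy outcomes.

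The outcomes text after Table 2 lists the harms of plasma to be assessed. They are venous thromboembolism and four harms tied to transfusion: "transfusion-related allergic reactions, febrile non-hemolytic transfusion reaction, delayed-serological transfusion reactions, and transfusion-associated circulatory overload".

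For binary outcomes, Statistical Analysis plans a relative risk with a 95% CI from a log-binomial model, or a Poisson model if the first does not converge. Sample Size says that "we do not provide a power analysis for any outcomes since no formal hypothesis testing will be conducted". Estimates, intervals and Bayesian probabilities are therefore what the trial will report, and they are meant to inform a larger trial.

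**The concern.** The plan justifies excluding large effects on the ground that medical interventions almost never produce them. That is reasonable for mortality or ICU-free days. It is weak for a reaction that requires a transfusion. Under Intervention, every plasma patient is assigned a blood product. Under Control, the initial dose is balanced crystalloid. A control can have such a reaction only after red cells, which Co-interventions allows in both groups, or after a product given at the clinician's discretion. A large relative risk is thus plausible from the design itself, and that is the region to which the prior gives little or no weight.

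Shrinkage toward no effect is conservative when the claim is benefit. When the claim is harm, it works in the reassuring direction. In a 26-patient pilot, a few reactions in the plasma arm and none in controls is a result one could well see. It would be reported with a lower probability of harm and a smaller relative risk than the data alone suggest, and those figures would pass to the designers of the next trial.

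**Working it through.** **Figures stated in the plan.** Sample Size: "We propose to enroll 26 patients (13 in each treatment arm"; 2 × 13 = 26. Randomization: "in 5 blocks of 4 and 1 block of 6 for a total of 26 patients"; 5 × 4 + 6 = 26. Both reproduce. There is no power calculation, prior width, expected reaction rate or probability threshold to reproduce.

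**Assumptions, none of them from the plan.** Four prior 95% ranges for the relative risk (RR): 0.5-2, 0.33-3, 0.2-5 and 0.1-10. Control risk p0 ~ Beta(0.5, 0.5). Event counts are illustrative.

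**Model.** Let θ = ln RR and p1 = p0·exp(θ), with θ ~ N(0, s²) and s = ln(U)/1.96, where U is the upper limit of the prior range:
- U = 2: 0.693/1.96 = 0.354
- U = 3: 1.099/1.96 = 0.561
- U = 5: 1.609/1.96 = 0.821
- U = 10: 2.303/1.96 = 1.175

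The likelihood for k1 plasma and k0 control events is p1^k1 (1−p1)^(13−k1) × p0^k0 (1−p0)^(13−k0). P(harm) is the posterior probability that θ > 0, computed on a grid. The comparator puts independent Beta(0.5, 0.5) (Jeffreys) priors on the two risks, so that each posterior is Beta(k + 0.5, 13.5 − k).

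| Plasma v control events | 0.5-2 | 0.33-3 | 0.2-5 | 0.1-10 | Independent Jeffreys |
|---|---|---|---|---|---|
| 3 v 0, P(harm) | 0.68 | 0.76 | 0.82 | 0.87 | 0.97 |
| 4 v 0, P(harm) | 0.75 | 0.84 | 0.90 | 0.93 | 0.99 |
| 4 v 0, posterior median RR | 1.25 | 1.6 | 2.1 | 3.0 | not computed |

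**Does P(harm) respond to the data?** Yes. Under the narrowest prior it is 0.19 at 0 v 4, 0.75 at 4 v 0, 0.95 at 8 v 0 and above 0.99 at 13 v 0.

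**Sensitivity to the set-up.** With control-risk priors Beta(1, 1) or Beta(1, 9) and a vague N(0, SD 5) comparator on ln RR, 3 v 0 gives 66-71% under the 0.5-2 prior against 90-95%. The posterior median RR is 1.15-1.21 against 3.7-5.5. On the odds-ratio scale the 0.5-2 prior gives 65-70% at 3 v 0. If exclusion is taken literally, as a uniform prior on ln RR with hard limits at RR 0.5 and 2, 3 v 0 gives 70-76%. The estimated RR then cannot exceed 2: even at 13 v 0 its median is about 1.9.

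**The frequentist backup.** With k0 = 0 the maximum-likelihood control risk is 0/13 = 0, so the estimated RR is (k1/13)/0. It has no finite value, and neither planned model gives a usable interval. The plasma-arm proportion has no such problem. Its exact 95% interval is 5% to 54% for 3/13 = 23%, and 0% to 25% for 0/13.

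**Low reaction rates.** Take 0.95 as an illustrative threshold and suppose that controls have no events. The Jeffreys analysis gives 0.93 at 2 v 0 and 0.97 at 3 v 0, so it needs at least 3 plasma events. P(X ≥ 3) for X ~ Bin(13, p) is 0.2% at p = 2%, 2.5% at 5% and 13% at 10%. At 10%, the neutral priors reach the threshold in at most 1% of trials.

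**The case against.** The strongest reply has four parts.

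- **The size of the pull cannot be derived from the plan.** No width is stated, and the text speaks of priors in the plural, so outcome-specific scales are not ruled out. This stands as a limit on the numbers. It does not remove the point, because the description in Statistical Analysis covers all the priors, for benefits and harms alike, and P(harm) at 3 v 0 and 4 v 0 was below the comparator at every width tried.
- **Controls may be transfused.** Red cells are allowed in both arms and later fluids are discretionary. A reader might infer that the arms can only differ greatly. The documents do not support that: no passage shows control exposure to be near zero, low reaction rates could give 0 v 0, and venous thromboembolism can occur in either arm. A large relative risk is plausible by design, not certain.
- **P(harm) is not the only safety result.** Effect estimates with 95% CIs are planned for all measures, and a risk/safety evaluation is set at 13 randomized patients. Both are true. The first gives little help in the zero-control-event case shown above.
- **Replacing the neutral prior is partly a preference.** Under independent Jeffreys priors a single reaction (1 v 0) already gives P(harm) of about 0.83. This stands, and is why the wider prior should be shown beside the neutral one and not in its place.

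**Conclusion.** The point holds in limited form. For the four transfusion-specific harms, a neutral prior that excludes large effects understates both the probability and the size of harm when events are few, and the plan does not state its width. At 3 v 0 the illustrative P(harm) is 0.68 to 0.87 against 0.97, a shortfall of 0.10 to 0.29. At 4 v 0 it is 0.75 to 0.93 against 0.99, a shortfall of 0.06 to 0.24. These figures rest on assumed prior widths, assumed counts and a Jeffreys prior on the control risk.

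Two stronger readings are tempting and should not be drawn. One is that P(harm) stays near 50% whatever the data show. The pull is partial, and 8 v 0 gives at least 0.95 under every width in the table. The other is that a cluster of reactions would be reported with a relative risk near 1. At 4 v 0 that describes only the narrowest prior (1.25); the others give 1.6 to 3.0. Nor would another prior make the trial able to detect uncommon reactions. At low rates, 26 patients are too few under any prior.

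The change is worth making because it is specific and nearly free, and the estimates are meant to shape a later trial.

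**What to change.** In Sample Size and Statistical Analysis, state the neutral prior numerically (distribution, effect scale, 95% range and control-risk prior), and add text on these lines:

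> For transfusion-specific harms, the plasma-arm risk will be reported with an exact 95% interval, and the risk difference between arms with a 95% interval by a method that is valid when an arm has no events. The probability of harm will be reported under the neutral prior and, beside it, under a weakly informative prior that does not exclude large effects (for example, independent Beta(0.5, 0.5) priors on each arm's risk).

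Keep the neutral prior for efficacy outcomes and mortality. Keep it also for venous thromboembolism, with the same sensitivity prior shown beside it. Fix both priors before outcome data are seen by arm.

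The cost is a few sentences and a second Bayesian run on data already to be collected; no further patients or measurements are needed. The downside is that the less shrunken probabilities vary more and can make one or two chance events look important. Labelling them as a sensitivity result beside the neutral-prior figure, with the event counts, deals with that.
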